Aim 4. Mediation by brain biomarkers. To examine whether CBF and glucose utilization mediate HBOT effects on cognitive function. Hypothesis: inclusion of the biomarkers in a mediation model will attenuate the effect of HBOT on cognition, suggesting them as underlying mechanisms.

We propose an RCT examining the short and long-term efficacy of HBOT, a therapy with strong biological plausibility for affecting beneficially impaired cognition *through vascular mechanisms, in elderly with T2D-related MCI, who are enriched in cerebrovascular disease and are at high dementia risk*. We focus on both cognitive and biomarker outcomes, providing context for identifying relevant mechanisms, and explore factors associated with HBOT efficacy, suggesting subgroups who may most benefit from the therapy. The study will be performed in Israel, with optimal infrastructure and expertise for all the study components at significantly lower costs. *HBOT can be widely deployed in the US so if successful, this pilot study will provide the basis for a multi-center large-scale clinical trial for definitive evidence of its benefits to cognition in T2D patients at high dementia risk. With the current lack of effective treatments for dementia while the proportion of elderly increases, the accelerating prevalence of T2D and dementia amplify this application's public health impact.*

B. SIGNIFICANCE

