Aims 2a and 2b: CBF and cerebral glucose utilization will be analyzed with a similar strategy to Aims 1a and 1b except that there will be no 6 month assessment. Mixed effects ANCOVA models will be used to compare changes in these outcome measures from baseline to 12 weeks following treatment, and, as exploratory analyses, linear mixed effects models will be used to assess relationships between treatment group (fixed effect) and the longitudinal trend (random intercept and slope for each subject) in MRI-ASL and FDG-PET outcome measures, assessed at 12-weeks and 12 months following treatment. Vascular effects of HBOT vs. Sham: Since CBF derived from ASL perfusion may represent combined effects of neural metabolism and vascular effects, a secondary mixed effects ANCOVA model (similar to Aim 2b) of vascular changes from baseline to 12 weeks as measured by ASL CBF will adjust for neural metabolism derived from FDG-PET.

Aim 3: Outcome measures (changes in CBF and cerebral glucose utilization) identified as having significant associations with treatment group in Aims 2a and 2b will be further explored as mediators of the relationship between treatment group and the change in cognition. To ensure that measurement of mediator

variables precedes measurement of cognition, we will define the outcome as the change in cognition from baseline to 12 months, and the mediators as changes in CBF and cerebral glucose utilization, from baseline to 12 weeks. The product of coefficients approach will be used within a multiple mediator modeling framework to provide point estimates of both the specific indirect effect (i.e. the effect of treatment group on the change in cognition from baseline to 12 months via a mediator among other mediators in the model) and the total indirect effect (i.e. the sum of specific indirect effects for all mediators in the model). The bootstrapping method⁹³ will be used in each multiple mediator model to compute bias-corrected standard errors (and 95% confidence intervals) for the specific and total indirect effect point estimates.

D7. Power Analysis and sample size justification

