Aim 1. Power is presented for detecting the difference in mean change (from baseline to 12 weeks) in overall cognition z-scores between the sham and HBOT treatment groups. Power calculations are based on two-sample t-tests and are conducted with a 2-sided 5% significance level (**Table 3**). A 2-sample t-test provides a more conservative power estimate than the proposed mixed model approach, which is expected to explain more variability and thus have more power to detect the same effect size with the same sample size.

The predicted mean change in the sham group from baseline to 12 weeks is -0.02 (based on the IDCD 12-week change in overall cognition). Assuming an SD of 0.50 in both the sham and HBOT groups, with a minimum sample size of 67 patients per arm, we have 80% power to detect an improvement in the HBOT group of 0.224, a “medium” effect size of 0.49. To account for an anticipated dropout rate of 13% (a reasonable estimate compared to the 5% dropout rate in our stroke study), we plan to enroll 77 patients per group for a total of 154 patients. Our HBOT trial years after mild traumatic brain injury⁷⁴ had an effect size of 0.47 for information speed processing which is clinically comparable to our primary outcome measure of overall cognition, and our HBOT trial on stroke patients⁷⁸ showed an effect size of 0.49 for the National Institutes of Health stroke scale, suggesting our detectable effect size of 0.49 is feasible.

Aim 2: As for Aim 1, power is presented for detecting the difference in the mean changes in CBF velocity and cerebral glucose utilization between the Sham and HBOT groups. Assuming a mean change in CBF velocity of -0.45 in the Sham group and an SD of 5.6 in both groups, with a minimum sample size of 67 patients per arm we have 80% power to detect an improvement in the HBOT group of 2.28, an effect size of 0.49. *To account for an anticipated dropout rate of 13%, we plan to enroll 77 patients per group for a total of 154 patients.* For cerebral glucose utilization, assuming a mean change in the sham group of -0.08 and an SD of 4.40 in both groups, with

Table 3: Two group t-test of equal means, equal n's)*			
	Outcome		
	Overall Cognition z-score	CBFV [†]	CGU [‡]
Sham Mean Change, D ₁	-0.020	-0.450	-0.08
HBOT Mean Change, D ₂	0.224	2.28	2.065
Difference in means, D ₁ -D ₂	-0.244	-2.73	-2.145
HBOT SD	0.50	5.60	4.40
Minimum N per group	67	67	67
Enrollment N per group**	77	77	77

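### Screening biomarkers on Aim 2 significance before mediation drops true mediators in about a third of trials and inflates the specific indirect effects that remain

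*Combined protocol and SAP*

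**What the plan says.** Aim 4 in the Specific Aims is "To examine whether CBF and glucose utilization mediate HBOT effects on cognitive function". It carries a hypothesis and sets no condition for either biomarker to be examined.

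Section D6 of the combined protocol and SAP, where mediation is labelled Aim 3, sets a condition. The measures that go forward are those "identified as having significant associations with treatment group in Aims 2a and 2b will be further explored as mediators". It defines "the mediators as changes in CBF and cerebral glucose utilization, from baseline to 12 weeks", and the outcome as the change in cognition from baseline to 12 months. On estimation it says: "The product of coefficients approach will be used within a multiple mediator modeling framework". The total indirect effect is "the sum of specific indirect effects for all mediators in the model". Bootstrapping "will be used in each multiple mediator model to compute bias-corrected standard errors" and 95% confidence intervals.

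D6 gives no threshold for significance in this step. It describes no mediation model without the screen, no correction for selection, and no repeat of the screen inside the bootstrap. Section D7 powers both biomarkers at 80% with 67 patients per arm.

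**The concern.** The screen tests the treatment effect on the 12-week biomarker change. The same contrast, in the same patients, is the treatment-to-mediator path in the product of coefficients. Two things follow.

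First, a true mediator that misses significance leaves the model, and its share leaves the total indirect effect. A question asked about two biomarkers becomes a question about one, or is not addressed. At 80% power, a non-significant result is weak evidence that treatment does not move the biomarker.

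Second, a biomarker enters only when its observed treatment effect is large, so the retained specific indirect effects are too large on average. If the two biomarkers are correlated and only one enters, it also absorbs part of the effect of the one left out.

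This matters because section D8 says that what the pilot shows about effect sizes and biomarkers will inform a larger multi-center trial.

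**Working it through.** **Inputs from the plan (D7 and Table 3).** Evaluable patients: 67 per arm. CBF: sham −0.45, HBOT 2.28, SD 5.6. Glucose utilization: sham −0.08, HBOT 2.065, SD 4.40. The power calculations "are conducted with a 2-sided 5% significance level"; I assume the same level for the screen.

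**Reproducing the plan's figure.**
- CBF: d = (2.28 + 0.45)/5.6 = 2.73/5.6 = 0.4875.
- Glucose utilization: d = (2.065 + 0.08)/4.40 = 2.145/4.40 = 0.4875.
- Power of a two-sample t-test with 67 per arm (noncentral t): 0.7998. This agrees with D7: "we have 80% power to detect an improvement in the HBOT group of 2.28".

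**Exclusion of true mediators at the design effect.** The chance of passing the screen is the power of the test.
- One given mediator excluded: 1 − 0.7998 = 0.200.
- At least one of two excluded, if independent: 1 − 0.7998² = 1 − 0.640 = 0.360.
- Both excluded, if independent: 0.2002² = 0.040.
- With residual correlation 0.5 (simulation, 6,000 trials), both pass in 0.690 and neither in 0.087. At least one is therefore excluded in 31% and both in about 9%.

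**Inflation of the treatment-to-mediator path.** To pass, the observed difference must exceed about 1.96 × √(2/67) = 0.339 SD, which is about 1.90 for CBF and 1.49 for glucose utilization. Write m = d√(n/2) = 0.4875 × √33.5 = 2.82. With φ and Φ the standard normal density and distribution function, and ignoring the negligible wrong-direction tail:

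E[estimate | significant]/truth = 1 + φ(1.96 − m)/[m Φ(m − 1.96)] = 1 + 0.275/(2.82 × 0.806) ≈ 1.12.

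**Indirect effects.** Simulation with two true mediators, 67 per arm and 6,000 trials per setting. The mediator-to-outcome slope of 0.3 and the correlations are assumptions. Entries are ratios of the mean estimate to the truth at d = 0.49; the total is averaged over trials in which at least one mediator passes.

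| Correlation | Both entered, specific | Screened, specific | Only one passes, specific | Screened, total |
|---|---|---|---|---|
| 0 | 1.00 | 1.12 | 1.10 | 0.93 |
| 0.3 | 1.00 | 1.18 | 1.34 | 1.00 |
| 0.5 | 1.00 | 1.19 | 1.44 | 1.04 |

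**Sensitivity. None of these settings is the plan's own.**
- d = 0.40, 67 per arm: power 0.632. At least one excluded 1 − 0.632² = 0.60; both 0.368² = 0.14; path inflated by about 26%.
- d = 0.35, same simulation: screened specific effects 1.37 to 1.58 times the truth; total 0.93 to 1.20.
- No dropout, 77 per arm, d = 0.49: power 0.860 (normal approximation). At least one excluded 1 − 0.860² = 0.26.
- Baseline adjustment, if baseline correlates r with change: d becomes 0.4875/√(1 − r²), which is 0.511 at r = 0.3 and 0.563 at r = 0.5. At least one excluded falls to about 30% and 19%.

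**The case against.** The strongest reply is that the screen does something useful. A treatment effect on the biomarker is necessary for mediation, so requiring evidence of one guards against false claims. A reader might infer that the screen adds nothing because the bootstrap already carries the uncertainty in that path. The calculations do not support that. With no treatment-to-mediator effect, simulation put the false-positive rate of the unscreened bias-corrected interval at about 7% to 9%, against about 4.5% to 6% with the screen (assumed slope 0.3 to 0.5). This part stands, and the fix has to allow for it.

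A reader might also take the 36% as lost findings. It is not. About three quarters of true mediators that fail the screen would have had an unscreened interval covering zero. At the design effect, detection of a specific indirect effect falls from about 80% to between 73% and 76%. The main loss is of reported estimates.

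The size also depends on the model. D7 calls the t-test conservative relative to the mixed model that will do the screening, so the real pass rate may be higher. Clustering, missing scans and testing several PET regions are not in these figures and would also change it. Independence is doubtful, since D6 itself says that ASL flow may reflect neural metabolism as well as vascular effects; hence the range over correlations.

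Finally, D6 speaks only of exploring mediators, in a pilot. That limits the weight of the point, but mediation is still a named aim with a hypothesis.

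**Conclusion.** The point holds as a moderate weakness in the mediation analysis. At the plan's own effect size, with the screen taken as an unadjusted two-sided 5% test, each true mediator is left out about one time in five. At least one of two is left out in about 31% to 36% of trials, and both in 4% to 9%. Retained specific indirect effects are about 12% to 19% too large on average, given the assumed slope and correlations. Smaller true effects make this worse; covariate adjustment or less dropout makes it milder.

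Three stronger readings are not supported:
- That all indirect effects are inflated. At the design effect the total is 0.93 to 1.04 times the truth, because a dropped mediator takes its share with it.
- That the intervals are badly wrong. Simulated coverage for retained mediators stayed near 95% at the design effect.
- That the aim is likely to be abandoned altogether. At the design effect that happens in 4% to 9% of trials.

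The primary cognitive analysis and the Aim 2 biomarker comparisons are unaffected.

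**What to change.** Fix the mediator set first; deleting the screening clause is not enough. Section D2j extracts FDG uptake from three regions, and the Specific Aims list 4D Flow as well as ASL, so D6 does not say which variables would enter. Name one CBF measure (ASL, which D2h gives as the CBF outcome) and one FDG summary, before treatment groups are unblinded.

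Make the main mediation analysis the model with both, entered whatever their Aim 2 p-values, and report specific and total indirect effects with bootstrap intervals. Keep the screened model only as a sensitivity analysis, with its threshold stated and the screen repeated inside each bootstrap sample. Report percentile intervals beside the bias-corrected ones, since dropping the screen gives up some protection against false mediation claims. Align the aim numbers, because mediation is Aim 4 in the Specific Aims and Aim 3 in D6.

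The cost is a short SAP amendment and some extra programming. No further patients, visits or scans are needed.

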[name], our neuroimaging collaborator, compared CBF using arterial spin labeling perfusion MRI (ASL-MRI) in middle-aged adults (n=69; mean age=60.4) with and without the metabolic syndrome (a pre-T2D condition). Mean gray matter CBF was 15% lower in the metabolic syndrome group (Figure 4). Voxel-wise image analysis indicated that this decrease pertained to a large portion of the cortical surface. The poorer memory in the metabolic syndrome group was partially mediated by CBF. These findings demonstrate feasibility of the proposed ASL-MRI and its sensitivity to the pre-

T2D metabolic syndrome supporting Aim 2a.

D1e. Insulin resistance is associated with poorer brain glucose uptake- [name] group examined the association of insulin resistance (using HOMA-IR) with global and regional FDG-PET uptake in 150 middle-aged adults. Higher insulin resistance (a pre-T2D condition) was associated with lower FDG-PET uptake (**Figure 5**); uptake in regions more strongly associated with insulin resistance (such as medial temporal lobe) was associated with cognitive function (**Figure 6**). These results show relationships of a T2D characteristic (insulin resistance) with regional glucose uptake supporting its use as a biological outcome in the proposed study.

[figure not shown]

Figure 5- The association between higher HOMA-IR and lower regional FDG-PET uptake in 150 late middle-aged adults ($p<.05$ FWE). Uptake values were adjusted for age, sex, family history status, APOE4, and glucose metabolism in the reference region. The color bar depicts t-values. Brains are oriented in neurological space. FWE= family-wise error corrected.

[figure not shown]

Figure 6- (A-B) Higher FDG-PET in left medial temporal lobe predicted better performance on verbal learning and immediate memory. (C-D) Left medial temporal uptake was not associated with working memory, but was associated with the speed and flexibility factor. Signal was adjusted by the FDG reference region, age, sex, APOE4, and family history status, and HOMA-IR. * $=p<.05$; ** $=p<.001$. JAMA Neuro

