D6. Statistical Analysis Plan- Efficacy analyses will be performed for the intent-to-treat (ITT) population, our primary analysis, and for fully and partially compliant per-protocol (PP) populations. The ITT population will include all participants in the group to which they were randomized, regardless of any protocol deviation including non-compliance, adverse events, or loss of follow-up. The PP populations will include participants in the group according to the intervention actually received, but a separate analysis will be performed for those who were fully compliant (at least 80% of sessions completed) and for those who were partially compliant (at least one session completed). A complier-average causal effect (CACE) analysis using a latent class modeling approach will also be performed on both fully and partially compliant populations. Patients missing a baseline value of a continuous efficacy outcome measure will be excluded from all analyses and maximum likelihood estimation methods will be used to handle missing data arising from an unobserved follow-up visit¹²².

Aims 1a and 1b: The primary (overall cognition) and secondary (executive functions, episodic memory domains, and computer-based tests) cognitive outcome measures (all summaries of z-scores), will each be analyzed using a mixed model analysis of covariance (ANCOVA) with time of assessment (baseline or 12 weeks) as the within-subjects factor, treatment group (HBOT vs. sham) as the between-subjects factor and baseline value of the outcome measure as the covariate. *Both, subject and 'cluster' (the variable used to identify to which group of at least 3 subjects each individual is assigned) will be modeled as random effects to account for the correlation among repeated measurements made over time within a subject as well as potential 'cluster effects' arising from blocks of at least 3 patients receiving treatment at a particular time after randomization.* An interaction term between time of assessment and treatment group will be included in each model allowing for estimation of the mean change from baseline to 12 weeks in each treatment group as well as a test for difference

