in change scores between groups. A test of parallel treatment effects across the range of baseline values will be conducted by including a three-way interaction term among time of assessment, treatment group and baseline value of the outcome variable as well as all lower order two-way interaction terms. If the three-way interaction term is statistically significant it will be retained in the final model and estimates of the difference in mean change scores between treatment groups will be evaluated at selected percentiles of the baseline distribution. Secondary mixed model ANCOVA analyses will be performed for cognitive assessments at 6 and 12 months following treatment. As an exploratory analysis, linear mixed effects models will assess the relationship between treatment group (fixed effect) and the longitudinal trend (random intercept and slope for each subject) in the primary and secondary cognitive outcome measures, assessed at 12-weeks, 6 months and 12 months following treatment. The primary hypothesis will be tested by assessing the interaction between treatment group and time of cognitive follow-up assessment, with a significant interaction indicating a difference in longitudinal cognitive trends between treatment groups. Potential confounders (age, gender, education, *duration of T2D, HbA1c, diabetes medications [insulin vs. no medications and oral agents vs. no medication], levels of atrophy and white matter hyperintensities*) will be included as covariates if there is imbalance at baseline ($p<0.1$) or association between the covariate and the response ($p<0.15$).

To explore whether specific dichotomized T2D characteristics (such as the last HbA1c level (dichotomized at 7) in the Diabetes Registry, the number of T2D complications, and the number of severe hypoglycemic episodes in the year preceding randomization) are associated with greater improvements following treatment with HBOT, mixed effects ANCOVA models similar to those for Aims 1 and 2 will add a main effect for the specific T2D characteristic and an interaction term between treatment group and the characteristic. Using the MHS dataset, we will also explore associations of dosage of the most prevalently used medications with cognitive outcomes. When potential confounders are associated with cognitive outcomes, this also may identify subgroups for which HBOT is particularly effective.

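### The mediation paragraph specifies raw change scores and names no baseline or mediator–outcome confounder adjustment, so an indirect effect could be biased if HBOT changes CBF or FDG uptake

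*Combined protocol and SAP*

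**What the plan says.** The mediation analysis is described in section D6 under Aim 3, which corresponds to Aim 4 on the aims page.

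- **Variables.** The plan will "define the outcome as the change in cognition from baseline to 12 months, and the mediators as changes in CBF and cerebral glucose utilization", with the mediator changes taken from baseline to 12 weeks.
- **Estimator.** "The product of coefficients approach will be used within a multiple mediator modeling framework", with bootstrap standard errors and confidence intervals for the specific and total indirect effects.
- **Entry rule.** Only biomarkers "identified as having significant associations with treatment group in Aims 2a and 2b will be further explored as mediators".
- **Covariates.** The paragraph names none, and it neither requires nor rules out baseline adjustment.

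Adjustment is described elsewhere in D6. The Aims 1a and 1b models take the "baseline value of the outcome measure as the covariate". The same text lists "Potential confounders (age, gender, education", T2D duration, HbA1c, diabetes medication, atrophy and white matter hyperintensities (WMH). These "will be included as covariates if there is imbalance at baseline" (p<0.1) or if associated with the response (p<0.15). For Aim 2, "CBF and cerebral glucose utilization will be analyzed with a similar strategy to Aims 1a and 1b". No such linking sentence covers the mediation model.

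**The concern.** Treatment is randomised but the mediators are not. The regression of cognitive change on biomarker change is an observational comparison, even inside a randomised trial. Measuring the mediators at 12 weeks and cognition at 12 months fixes the order of measurement. It does not remove common causes of both.

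The documents describe a plausible common cause. Section B3a presents T2D and metabolic disease as lowering CBF and impairing cognition through cerebrovascular damage, and section D1 reports that "The poorer memory in the metabolic syndrome group was partially mediated by CBF". A subject with worse vascular disease may lose both CBF and cognition faster, whether or not one change drives the other. Raw change scores add a second route: if baseline CBF and baseline cognition are correlated, regression to the mean makes the two changes correlated as well.

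The aims page says attenuation of the HBOT effect by the biomarkers would suggest them as underlying mechanisms. A confounded mediator slope can produce that attenuation. What is at stake is the mechanistic reading that would feed the larger trial planned in D8, not the efficacy result.

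**Working it through.** **1. The plan's own figures (D7, Table 3).**
- Cognition: 0.244/0.50 = 0.488; a two-sample t-test at 67 per arm has 80.1% power.
- CBF: 2.73/5.6 = 0.4875; power at 67 per arm is 80.0%.

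Both reproduce. The plan gives no power or error figure for mediation. Evaluable total: 2 × 67 = 134.

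**2. Assumptions that the documents do not supply.**
- Visit-to-visit correlation 0.7 for each measure, in units of the baseline SD.
- Baseline CBF–cognition correlation r0 of 0.3 or 0.5.
- A shared factor, independent of both baselines, correlating c = 0.2 or 0.3 with each change.
- True effect of the mediator on cognition is zero; one mediator; cluster effect ignored.

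**3. Spurious correlation of the two changes within arm.**
- Variance of a change = 2 × (1 − 0.7) = 0.6.
- Covariance passed on by the baselines = (1 − 0.7)² × r0 = 0.09 r0, so the correlation is 0.09 r0/0.6 = 0.15 r0.
- The shared factor adds c². In total, ρ = 0.15 r0 + c².

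**4. False-positive rate of the mediator path.** The standard error of the slope is about 1/√(134 − 3) = 0.087. The rate is P(|Z + ρ/0.087| > 1.96). Multiplying by about 0.80, the chance that the treatment-to-mediator path is significant at the planned CBF effect, gives the rate for both paths together.

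| r0 | c | ρ | Mediator path | Both paths |
|---|---|---|---|---|
| 0 | 0 | 0 | 5% | 4% |
| 0.3 | 0 | 0.045 | 8% | 6.5% |
| 0.5 | 0 | 0.075 | 14% | 11% |
| 0.3 | 0.2 | 0.085 | 16% | 13% |
| 0.3 | 0.3 | 0.135 | 34% | 28% |

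Simulations of the same set-up agree. In the four non-null rows they gave 8–9%, 13–15%, 16–17% and 33–35% for the mediator path, and about 7%, 10%, 13% and 27% for both paths.

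**5. Size of the spurious indirect effect.** With the Table 3 inputs, and the 12-week SD of 0.50 assumed to hold at 12 months, it is 2.73 × ρ × 0.50/5.6 = 0.244ρ. For ρ = 0.045 to 0.135 that is 0.011 to 0.033, or about 5% to 13% of the planned 0.244 difference.

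**6. What adjustment removes.** Adjusting for both baselines removes the 0.15 r0 part. It leaves a partial correlation of c²/0.85, where 0.85 = 0.51/0.6 is the share of change variance remaining after the baselines (0.51 = 1 − 0.7²). That is 0.047 or 0.106, and false-positive rates of about 8% and 22–23%. Adding the shared factor as a covariate returns the rate to about 5%.

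**7. Check with the planned type of interval.** A bias-corrected bootstrap at 67 per arm, among trials passing the entry rule with a true CBF effect of 2.73, falsely excluded zero in 8%, 29%, 71% and 97% of trials at ρ = 0, 0.1, 0.2 and 0.3. With the shared cause in both path models it was 6–9%. The larger ρ values need a strong factor: ρ = 0.3 from a shared cause alone means it correlates √0.3 = 0.55 with each change.

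**8. When HBOT does not change CBF.** The entry rule then passes in only about 5–6% of trials, so false mediation stays at or below about 6% overall.

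**The case against.** **The plan is silent; it does not exclude adjustment.** This stands. A reader might infer that the SAP has ruled out covariates, or that treatment is the only other term in the outcome model. Neither is written. The framework is a multiple-mediator one, so CBF and FDG would enter together if both pass the entry rule. The same SAP adjusts for baseline, lists vascular confounders in the Aims 1a and 1b text, and in D2j uses WMH as a covariate in the imaging analysis. The supportable point is that nothing extends these rules to mediation.

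**The listed rule would catch a strong confounder.** Partly. A common cause of cognitive change would tend to meet the p<0.15 trigger. But the rule selects by p-value, was not designed to find causes of both mediator and outcome, and does not put baseline CBF or FDG into a model whose response is cognition.

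**The entry rule protects.** Only when HBOT has no effect on the biomarker. If it has the planned effect, about 80% of trials pass and the mediator path is no better protected among them. A reader might also infer that a shared vascular cause would by itself be reported as mediation. The documents do not support that: a treatment effect on the mediator is needed too.

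**The larger error rates rest on assumed correlations, and this is an exploratory aim of a pilot.** Both stand. The regression-to-the-mean route alone moves the rate from 5% to about 8% at r0 = 0.3. The aims page speaks only of suggesting mechanisms, so it would be wrong to say the trial will conclude that CBF and glucose utilization are the mechanisms.

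**Conclusion.** The concern holds in conditional form. As written, the mediation paragraph leaves the non-randomised path on raw change scores without specified adjustment. If HBOT changes CBF or FDG uptake, the indirect effect could be biased, upward where the shared cause moves both changes the same way.

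Under the assumptions above, false positives for the mediator path are about 8–14% from correlated baselines and about 16–35% with an added shared factor, or roughly 7–27% when both paths must be significant. These figures show sensitivity. They are not estimates for this trial, because the documents give none of the correlations.

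The plan should settle this before analysis, because a better model is available from data already being collected.

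**What to change.** In the D6 mediation paragraph:

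1. Model 12-month cognition and the 12-week mediators rather than raw changes, with treatment, baseline cognition, baseline CBF and baseline FDG in the path models.
2. Add a fixed set of covariates, not selected by p-value, from the D6 confounder list: age, sex, education, T2D duration, HbA1c, diabetes medication, atrophy and WMH, using baseline values.
3. State that the indirect effect assumes no unmeasured mediator–outcome confounding.
4. Add a simple sensitivity analysis showing how strong such confounding would have to be to remove the indirect effect.

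Baselines alone are not enough, as step 6 of the working shows.

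**Cost.** Three baselines plus eight covariates is 11 degrees of freedom, or 12 if medication takes the plan's two contrasts, from about 134 evaluable subjects. The rest is SAP wording and a little more analysis. The covariates are already collected. The primary efficacy analysis does not change.
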